6.4 Sample Size and Power

Sample size calculations were performed using PASS 16 sample size software and were based on preliminary data in 35 patients with available data on the AGS scale.

Analysis of the primary outcome, safety data including laboratory studies and adverse events, will be descriptive and include all individuals, available studies and AEs. Power

analysis is not possible for these analyses, since adverse events may be rare, even in the AGS population, and statistical comparisons may not be feasible.

We anticipate that we will have an evaluable sample size of ~45 treated patients. For the analysis of secondary outcomes, in our preliminary analysis when we compared the average of AGS scales prior to treatment (pre-treatment average) to the average of the AGS scale after treatment (post-treatment average), we observed that the average of within subject changes (post-treatment average minus pre-treatment average) was 0.80 (95% CI = 0.45, 1.16) and that the standard deviation of changes was 1.04. This corresponds to an effect-size of 0.80/1.04 = 0.77. From PASS 16, a sample size of 30 data pairs achieves 98.3% power to reject the null hypothesis of zero effect size when the population effect size is 0.77 and the significance level (alpha) is 0.050 using a twosided paired t-test. Should the effect-size be smaller than we observed in our preliminary data, we will have 80% power to detect an effect size of 0.53, which would correspond to an average of within subject changes of 0.55, if the SD of changes is 1.04. We will therefore have sufficient power to detect differences that are similar to those observed in preliminary data. For the more complex analyses that are proposed for the larger data set that contains the historical controls (>50), our power will be even greater.

Drop-Out: Overall, this clinical study may enroll up to 55 patients. However, power analysis suggest that an enrollment number of up to approximately 30 is required to obtain results for efficacy that are clinically meaningful, and accounting for those subjects who are found to be ineligible at screening, subjects withdrawn from participation for various reasons and those who are enrolled to this study who are not initially eligible at screening. In addition, some participants may be lost to follow up, or may not survive until one-year post-baseline, when the primary efficacy analysis will be conducted. Thus, we expect to be able to perform the necessary analysis even if there is significant drop out.

We will evaluate the reasons for drop-out carefully, especially with respect to the missing at random assumption that is required for GEE/QLS regression. As described above, a sample size of 30 patients will be adequate for analysis of our primary outcome. The goal of the secondary analyses will be primarily to inform the generation of hypotheses for future studies in this population.

The analysis of data obtained from this group of initially ineligible, but prospectively approved subjects entered to the study, will be assessed independently of the main group of subjects who meet all eligibility criteria. The statistical analysis within this group will depend on the total number of subjects in the group, as well as the degree of clinical heterogeneity of these patients. If the sample size is large enough we will attempt to replicate the analyses that are performed for the eligible participants in this group.

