6.3 Statistical Methods

6.3.1 Baseline Data and Descriptive Analysis

Baseline and demographic characteristics will be summarized overall by standard descriptive summaries (e.g. means and standard deviations for continuous variables such as age and percentages for categorical variables such as gender). In addition, demographic characteristics and clinical variables that are evaluated at the first encounter will be compared between subjects who are never treated, versus those who are eventually treated. Patients are not randomized to receive treatment (or not), so it is important to identify variables that are associated with an increased (or decreased) likelihood of receiving treatment. Chi-square tests will be used to compare categorical variables between groups. T-tests or tests of medians (for skewed variables) will be used to compare continuous variables between groups. Overlaid histograms will also be used to evaluate the distribution of continuous baseline variables between patients who were never treated, versus those who were eventually treated. In addition, Kaplan-Meier analysis with the log rank test will be used to compare the distribution of time to treatment between levels of categorical variables (e.g. group genotype) measured at baseline. In our preliminary analysis, we did not identify meaningful differences between patients who were never treated, versus those who were eventually treated.

We will conduct descriptive statistical analysis using inferential and graphical secondary data analytic techniques. The primary and secondary assessments will first be summarized by time of measurement. In addition, individual "spaghetti" plots will be generated for each assessment. Changes in primary and secondary outcomes from baseline (with 95% confidence intervals [CI]) will be calculated at specified time points, e.g. between baseline and 52 weeks. In addition, overall changes (final minus baseline) (with 95% CI) will be computed for primary and secondary outcomes. In addition to means (with 95% CI) we will also calculate median changes (with 25th to 75th

percentiles). Analyses will be conducted in Stata 18.0, with a p-value < 0.05 as the criterion for statistical significance.

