6.3.2 Primary Outcome Analysis

As is often the case in a study of a rare disease, we face a number of challenges in our analysis. The number of available patients with AGS is limited, so that our sample size is small. This protocol grew out of a compassionate use trial, so that randomization could not be employed to assign patients to receive treatment (or not). The temporal spacing of measurements differs between treated patients versus historical controls. As a result of these features, there are limitations to many of the standard statistical approaches. Our approach will therefore be to apply a recommended approach for efficacy, but to also apply several sensitivity analyses. Our goal will be to demonstrate efficacy for several statistical approaches, as we achieved in our analysis of preliminary data.

Our efficacy analysis for our primary outcome will apply the method described in Section 15.4 of Fitzmaurice, Laird, & Ware⁷⁴ that decomposes longitudinal effects of treatment versus cross-sectional effects due to participants starting treatment at different ages. We will first create a time for each patient that is negative prior to treatment and is positive after treatment. We will then fit a GEE model that includes time within patients, an indicator variable for treatment and a time by treatment interaction term. If the interaction term is significant, this will indicate that the change over time in AGS score (slope) is different after treatment, versus before. If the interaction term is not significant, it will be removed and the model will be fitted with time and the indicator variable for (post) treatment. If the indicator variable differs significantly from zero, this will indicate that the AGS score is higher on average, post-treatment. To compare values at baseline and 52 weeks post baseline, different parameterizations of time (continuous versus indicator variables at different visits) will be considered and analyses will also be performed on data restricted to values measured at baseline and 52 weeks post baseline. This approach will first be applied to patients who are eventually treated. to compare their AGS scores pre versus post-treatment.

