6.3.3 Secondary Outcome Analysis

6.3.3.1 Longitudinal analysis of the AGS scale

In secondary analysis, we will include historical controls in the GEE models described in section 6.3.2; the "age at treatment" (time zero) for controls will be their age at their final encounter. The GEE models will also adjust for confounders (e.g. age of the subject, length of disease, and genotype⁷⁵) especially variables that were identified as being related to receiving treatment (see Section 6.3.1). We will fit several working correlation structures to model the association between the repeated measurements on each patient, and will use goodness of fit criteria for GEE to choose between the structures. Goodness of fit criteria will also be used to compare fit of models (e.g. for models that include time as a continuous variable versus a series of indicator variables for visit).

In addition to GEE, we will fit quasi-least squares (QLS) regression models.⁷⁶ QLS is a computational approach for estimation of the correlation parameters in the framework of GEE that can be applied should GEE fail to converge, or to fit correlation structures that are not available in the framework of GEE. For example, the Markov correlation structure that is plausible for unequally spaced data is not available in the **xtgee** command for implemention of GEE in Stata.

In addition to the GEE analysis that includes historical controls, we will implement several sensitivity analyses that are described in the Table below. These methods were successfully implemented in analysis of our preliminary data.

Table 2. Statistical Approaches				
Question to be Evaluated in Sensitivity Analysis	Statistical Approach			
For each patient who was eventually treated, if we obtain their average of their AGS scale values prior to treatment (pre-treatment average) and the average of their AGS scale values after treatment (post- treatment average), are the post-treatment averages higher than the pre-treatment averages?	Compute the average of the within subject changes (post-treatment average minus pre-treatment average) with 95% CI; apply the paired t-test to compare the mean of pre-treatment to the mean of post-treatment averages within patients.			

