Is the average AGS scale value higher after treatment than before treatment, when we modify the previous analysis to include patients who were never treated, by calculating their pre-treatment average AGS scale as the average of all of their AGS scale values?	GEE analysis in which patients who were treated contribute two measurements (pre-treatment average and post-treatment average), while patients who were never treated contribute one measurement ("pre-treatment" average of AGS scale). The GEE model will include an indicator variable for post-treatment and use an exchangeable correlation structure to account for the intra- subject correlation of measurements on each patient.			
Does the AGS scale at screening differ from the final value within patients?	Paired t-tests or non parametrics Wilcoxon signed-rank test will be applied as appropriate to compare the screening and final values within patients.			

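### Section 6.4 tests drop-out against missing at random, which by itself does not make unweighted GEE/QLS valid, and section 6 plans no estimate of the 52-week AGS change that is valid under it

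*Combined protocol and SAP*

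**What the plan says.** The primary endpoint (6.1) is the change in the AGS scale from baseline to 52 weeks.

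- **Main model (6.3.2).** "We will then fit a GEE model that includes time within patients, an indicator variable for treatment and a time by treatment interaction term". No weighting and no working correlation structure are stated. For the 52-week comparison, several codings of time will be tried, and "analyses will also be performed on data restricted to values measured at baseline and 52 weeks post baseline".
- **Descriptive estimate (6.3.1).** "Changes in primary and secondary outcomes from baseline (with 95% confidence intervals [CI]) will be calculated at specified time points", with baseline to 52 weeks as the example.
- **Working correlation (6.3.3.1, secondary analysis).** Several structures will be fitted and the authors "will use goodness of fit criteria for GEE to choose between the structures". QLS is added as another way to estimate the correlation parameters.
- **Sensitivity analyses (Table 2).** Row 1: "Compute the average of the within subject changes (post-treatment average minus pre-treatment average) with 95% CI". Row 2 is a GEE in which "patients who were treated contribute two measurements (pre-treatment average and post-treatment average"). Row 3 compares screening with the final value.
- **Missing data (6.4).** The section foresees that "some participants may be lost to follow up, or may not survive until one-year post-baseline". It promises a careful look at the reasons for drop-out, "especially with respect to the missing at random assumption that is required for GEE/QLS regression".

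Section 6 mentions no weighted GEE, imputation or likelihood-based model.

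**The concern.** The 6.4 sentence sets the standard by which drop-out will be judged. If the review concludes that MAR is plausible, a reader will take the GEE result as safe. In general it is not. Unweighted GEE/QLS uses the observed scores as they stand. If leaving depends on earlier AGS scores, the later visit means are pulled towards the patients who stayed, unless the working covariance carries the right information from early to late visits.

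The two analyses nearest the endpoint are more exposed. They use baseline and week 52 only, so the interim scores that would explain who left are thrown away. Drop-out that is MAR in the full data is then no longer MAR in the data analysed.

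The study is single-arm and open-label, so there is no concurrent group in which the same distortion would cancel. At stake is the estimated 52-week change: too high if decliners leave, too low if improvers leave.

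**Working it through.** **1. The plan's own figure.** Paired t-test, n = 30, two-sided alpha 0.05, df = 29, noncentrality = d × √30.
- d = 0.77: 0.77 × 5.477 = 4.217, power 98.3% (6.4 states 98.3%).
- d = 0.53: 2.903, power 80.1% (stated 80%); 0.53 × 1.04 = 0.55.

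Both reproduce. The issue is bias, not power.

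**2. Assumptions of the illustration** (none is in the documents except the value 1.04):
- True mean change 0; AGS scores at 0, 6 and 12 months; baseline SD 1 to 3.5.
- Random slope SD 0.763 per year and residual SD 0.5, so the SD of the 52-week change = √(0.763² + 2 × 0.5²) = √(0.582 + 0.500) = 1.04. Section 6.4 gives 1.04 for the post-average minus pre-average contrast, so it is borrowed.
- After month 6, a patient whose score fell by 0.5 or more leaves with probability 40% or 60%; all others leave with probability 5%. This is MAR, because it depends only on observed scores.

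**3. Loss.** Variance of the 6-month change = 0.582 × 0.25 + 0.5 = 0.6455, SD 0.803. P(fall of at least 0.5) = Φ(-0.5/0.803) = Φ(-0.622) = 0.267.
- Loss at 40%: 0.05 + 0.35 × 0.267 = 14.3%.
- Loss at 60%: 0.05 + 0.55 × 0.267 = 19.7%.

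**4. Bias in complete baseline/week-52 pairs, by hand.** This is what a simple 52-week change in 6.3.1 amounts to.
- Covariance of the 6- and 12-month changes = 0.5 × 0.582 + 0.25 = 0.541; slope = 0.541/0.6455 = 0.838.
- Mean 6-month change in those who stay = (0.35 or 0.55) × 0.803 × φ(0.622) / (1 - loss), where 0.803 × φ(0.622) = 0.264.
- At 40%: 0.35 × 0.264/0.857 = 0.108; × 0.838 = **+0.09**.
- At 60%: 0.55 × 0.264/0.803 = 0.181; × 0.838 = **+0.15**.

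**5. Bias by simulation** (400,000 patients per setting):

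| Estimator of the 52-week change | Bias, AGS points |
|---|---|
| GEE, exchangeable, all visits | +0.04 to +0.07 |
| GEE, AR(1), all visits | -0.03 to 0.00 |
| GEE, unstructured, all visits | about +0.01 |
| GEE restricted to baseline and week 52 | +0.07 to +0.15 |
| Likelihood, unstructured covariance, all visits | 0.00 |

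Unstructured GEE is not exactly unbiased: it uses one common variance, while here the variance grows over time, and its correlations come from the observed scores only.

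**6. How far this depends on the assumptions.**
- SD of change 0.8 to 1.4 (12-23% lost): exchangeable +0.02 to +0.10, restricted +0.05 to +0.22.
- Other variance splits at SD 1.04: exchangeable +0.01 to +0.10, AR(1) -0.10 to +0.05, unstructured 0.00 to +0.05.
- Five three-monthly visits (the 5.2.4 schedule): exchangeable +0.04 to +0.06, AR(1) -0.03 to +0.02, unstructured +0.01 to +0.02.
- Improvers leave instead (60%, baseline SD 2): exchangeable -0.06, restricted -0.14.
- A separate set-up with five visits, true change 0.80 and 10-33% lost: likelihood 0.79-0.80, exchangeable 0.80-0.87, AR(1) 0.69-0.94, unstructured 0.79-0.85, independence 0.81-1.76.

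**The case against.** **The sentence can be read as naming a necessary condition.** It does not say that MAR is sufficient, so it is incomplete rather than plainly false. That is fair, but the gap remains: the review of drop-out would stop at a condition that does not settle whether the estimate is valid.

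**The main model may be little affected.** In runs of 45 patients, the 6.3.2 pre/post model with its structure picked by fit had a bias of +0.02 to +0.04, small beside the expected 0.80 and the detectable 0.55 in 6.4. This stands. Choosing by fit helps when the choice is close to the truth, though it cannot guarantee that. The larger figures belong to the restricted analysis, which 6.3.2 presents as additional but which matches the endpoint most closely.

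**Some planned analyses hold up.** Table 2 row 1, the contrast behind the power calculation, is nearly unbiased in this setting (-0.012 to +0.005). It averages all post-treatment visits, so it answers a different question from the week-52 change. Including the compassionate-use data (6.3.3.6, 9.7.1) limits the exclusion of patients. Sections 1.5 and 6.3.3.2 also say the scale can be scored from clinical notes, which could recover some missing values; the plan does not commit to doing so.

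**Stronger readings to resist.** A reader might infer that the trial is biased towards benefit, or that drop-out could manufacture the expected effect. The documents give no drop-out rate, mechanism or SD of the 52-week change, and the sign depends on who leaves. A reader might also treat the missing rule for deaths as a statistical error. It is an unstated choice of estimand, separate from this point.

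**Conclusion.** The point holds as a flaw in the stated assumption and a gap in the planned estimates. MAR alone does not protect unweighted GEE/QLS, and nothing in section 6 estimates the week-52 change in a way that is valid under MAR. Confidence in that is high.

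Confidence in the consequence is low. Under the stated assumptions the bias is small when all visits are used with a structure close to the truth. It reaches 0.15 points in the restricted analysis, or 0.15/0.55 = 27% of the change that 6.4 says can be detected with 80% power. Other assumptions widen the range or reverse the sign. The point should be corrected before analysis, but it gives no ground for saying that the planned conclusion would be overturned.

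**What to change.** 1. **Correct the sentence in 6.4.** State that unweighted GEE/QLS needs drop-out unrelated to past outcomes given the model covariates or, under MAR, a working covariance that is both correctly specified and consistently estimated.
2. **Add one model beside the planned GEE.** Estimate week 52 minus baseline from all scheduled visits with a likelihood-based mixed model in the planned Stata (`mixed`): visit indicators, unstructured residual covariance, REML, small-sample degrees of freedom. Name random intercept and slope as the fallback if it does not converge. Read the restricted baseline/week-52 result against it.

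**Cost.** SAP wording and one extra model; no new data. The model assumes approximate normality on a 0-11 scale, although in a check with rounded, bounded scores and the pilot case mix the likelihood estimate stayed within 0.001 of the truth. An unstructured covariance has 3 × 4/2 = 6 parameters with three visits or 5 × 6/2 = 15 with five, so the fallback may be needed at about 45 patients. Weighted GEE is less attractive: 14-20% of 45 is only 6-9 drop-outs on which to build the weights.

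**Secondary notes.** State how deaths before week 52 and the event in section 4.7 (starting another effective agent) enter the AGS analysis, and whether missing week-52 scores may be taken from clinical notes.

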7 STUDY MEDICATION (STUDY DEVICE OR OTHER STUDY INTERVENTION)

7.1 Description

7.1.1 Packaging

Baricitinib will be dispensed by the investigational pharmacy in labeled containers.

7.1.2 Labeling

Individual labeling for drug packaging will be provided by the investigational pharmacy.

7.1.3 Dosing

Baricitinib can be taken orally or administered via G-tube. Baricitinib should be handled with gloves by caretakers. Dosing will be performed according to dosing tables (Appendices 3 and 4).

7.1.4 Treatment Compliance and Adherence

Patient compliance with investigational product will be assessed at each visit. Compliance will be assessed by counting returned tablets. Patients found to be noncompliant per investigator judgment should be assessed to determine the reason for noncompliance and educated and/or managed as deemed appropriate by the investigator to improve compliance.

7.1.5 Drug Accountability

Adequate records of study drug receipt and disposition will be maintained by the CHOP Pharmacy. Records of receipts, investigational drug orders, dispensing records, and disposition forms will be examined during the course of the study. The purpose of these records is to ensure regulatory authorities that the investigational new drug will not be distributed to any person who is not a study subject under the terms and conditions set forth in this protocol. The study medication is to be prescribed by the Investigator or designee and may not be used for any purpose other than that described in this protocol.

8 SAFETY MANAGEMENT

The study protocol will be submitted to the FDA and will be reviewed by the study DSMB and the Medical Monitor. Participant enrollment may only begin after final IRB approval and FDA authorization to proceed.

8.1 Clinical Adverse Events

Clinical adverse events (AEs) will be monitored throughout the study.

8.2 Adverse Event Reporting

Unanticipated problems related to the research involving risks to subjects or others that occur during the course of this study (including SAEs) will be reported to the IRB in accordance with CHOP IRB SOP 408: Unanticipated Problems Involving Risks to Subjects. AEs that are not serious but that are notable and could involve risks to subjects will be summarized in narrative or other format and submitted to the IRB at the time of continuing review.

8.3 Definition of an Adverse Event

An adverse event is any untoward medical occurrence in a subject who has received an intervention (drug, biologic, or other intervention). The occurrence does not necessarily have to have a causal relationship with the treatment. An AE can therefore be any unfavorable or unintended sign (including an abnormal laboratory finding, for example), symptom, or disease temporally associated with the use of a medicinal product, whether or not considered related to the medicinal product.

All AEs (including serious AEs) will be noted in the study records and on the case report form with a full description including the nature, date of onset, determination of nonserious versus serious, intensity (mild, moderate, severe), duration, causality, and outcome of the event.

As defined in title 21 of the Code of Federal Regulations Part 312, an *adverse event* (*AE*) is "any untoward medical occurrence associated with the use of a drug, whether or not considered drug related". All adverse events will be classified using the current version of Common Terminology Criteria for Adverse Events (CTCAE), developed and maintained by CTEP at the National Cancer Institute.

A suspected adverse reaction is any adverse event for which there is a reasonable possibility that the drug caused the adverse event. "reasonable possibility" means that there is evidence, such as a temporal relationship, to suggest a causal relationship between administration of drug and the adverse events. It is less certain about causality than *adverse reaction*.

